### 5.2.2. Analyses for Categorical Endpoints

Categorical variables will be presented using summary statistics: number of observations and percentages.

### 5.2.3. Concentration-QTc analysis

PK/PD model will be established to characterize the relationship between sisunatovir plasma concentration and change from baseline in Fridericia's heart-rate corrected QT interval

$(\Delta QTcF)$  using the concentration-QTc analysis set. Based on the recommendation in the White Paper, the linear mixed effect model preferred is pre-specified as:

$$\Delta QTcF_{ijk} = \theta_0 + \eta_{0,i} + \theta_1 TRT_j + (\theta_2 + \eta_{1,i}) C_{ijk} + \theta_{3k} + \theta_4 (QTc_{ij0} - \overline{QTc_0}) + \varepsilon_{ijk}$$

$\Delta QTcF_{ijk}$  is the change from baseline in QTcF for participant  $i$  in treatment  $j$  at time  $k$ ;  $\theta_0$  is the population mean intercept in the absence of a treatment effect;  $\eta_{0,i}$  is the random effect associated with the intercept term  $\theta_0$ ;  $\theta_1$  is the fixed effect associated with treatment  $TRT_j$  (0 = placebo, 1 = sisunatovir);  $\theta_2$  is the population mean slope of the assumed linear association between plasma sisunatovir concentration and  $\Delta QTcF_{ijk}$ ;  $\eta_{1,i}$  is the random effect associated with the slope  $\theta_2$ ;  $C_{ijk}$  is the plasma concentration of sisunatovir for participant  $i$  in treatment  $j$  and time  $k$  and  $C_{ijk} = 0$  for placebo group;  $\theta_{3k}$  is the fixed effect associated with time, where time is a categorical factor; and  $\theta_4$  is the fixed effect associated with centered baseline  $QTcF_{ij0}$ , where  $\overline{QTc_0}$  is overall mean of  $QTcF_{ij0}$ , i.e., the mean of all the baseline (= time 0) QTcF values. It is assumed the random effects ( $\eta_{0,i}$ ,  $\eta_{1,i}$ ) are normally distributed with mean [0,0] and an unstructured covariance matrix, whereas the residuals  $\varepsilon_{ijk}$  are normally distributed with mean 0 and variance  $\sigma^2$ .

The final c-QTc model will be used to compute the placebo adjusted change from baseline QTcF ( $\Delta\Delta QTcF$ ) and corresponding two-sided 90% CI at concentrations of interest (e.g. expected  $C_{max}$  at the CCI and potentially high clinical exposures). The  $\Delta\Delta QTcF$  is the difference between the model-estimated  $\Delta QTcF$  at concentration of interest and the model-estimated  $\Delta QTcF$  for placebo (eg. concentration=0). If the upper bound of the two-sided 90% interval for the  $\Delta\Delta QTcF$  as estimated by the final concentration- $\Delta QTc$  model established in this study is <10 msec at the highest clinically relevant exposure, the absence of an effect of sisunatovir on QTc will be concluded.

### Evaluation of Assumptions - Linear Mixed Effect Model

Before proceeding to c-QTc modeling, the following four assumptions for the linear mixed effect model will be evaluated using exploratory plots based on the recommendation in the White Paper.

- Assumption 1: no drug effect on HR.

The time course of mean change from baseline in HR and placebo-adjusted HR by treatment will be plotted to evaluate the potential effect of sisunatovir on HR.

- Assumption 2: QTcF interval is independent of HR.

A scatterplot of QTcF vs. RR intervals by treatment and a QTcF-RR quantile plot will be generated to confirm the appropriateness of Fredericia's heart-rate correction method.

- Assumption 3: No time delay between drug concentration and  $\Delta QTcF$ .

PK/PD hysteresis will evaluated using following exploratory plots:

- Longitudinal plot of mean and 90% CI for  $\Delta QTcF$  and/or placebo-adjusted  $\Delta QTcF$  ( $\Delta\Delta QTcF$ ) and concentration of sisunatovir.

- Plot of mean  $\Delta\Delta QTc$  and concentration connected in temporal order for the sisunatovir treatment group.
- Scatter plot of paired  $\Delta\Delta QTcF$  and concentration for the sisunatovir treatment group.
- Assumption 4: Linear c-QTcF relationship.

The linearity will be assessed by a scatter plot of paired  $\Delta\Delta QTcF$  and concentration by treatment incorporating a trend line (eg, loess smooth or linear regression).

### Concentration-QTc Quantile Plot

A concentration-QTc quantile plot of observed data overlaid with the model predictions is a visual assessment of how well the model fits the data. In this plot, the observed drug concentrations are categorized into their deciles (eg, 10 bins of equal size) and the placebo-adjusted mean change from baseline QTcF intervals ( $\Delta\Delta QTcF$ ) are calculated for each bin, along with their 5th and 95th percentiles, as well as the 90% confidence interval for the mean

### Model Selection and Evaluation

If exploratory plots indicate the modeling assumptions for the linear model are not met, additional modeling steps will be performed to determine an appropriate c-QTc model.

- If there is a potential delay between sisunatovir concentration and the effect on QTcF, an alternative model with a delayed effect will be considered to account for the delay.
- If apparent relationship between QTcF and RR interval and/or differences distribution of HR between on- and off-drug conditions are observed in exploratory plots, other approaches to evaluate QT/QTc may be considered as summarized in the methodology paper by Garnett et al..
- If a linear relationship between drug concentration and the effect on QTcF is not supported by exploratory plots, or linear models cannot describe the observed data, nonlinear models may be explored to optimize the model fit, including Emax model described below or other types of PD models.

### Emax Model

The following Emax model may be fitted and assessed if the linear mixed model clearly does not capture the trend of the data in the concentration-QTcF quantile plot:

$$\Delta QTcF_{ijk} = \theta_0 + \eta_{0,i} + \theta_1 TRT_j + \frac{(\theta_{22} + \eta_{1,i})C_{ijk}}{\theta_{21} + C_{ijk}} + \theta_{3k} + \theta_4(QTc_{ij0} - \overline{QTc_0}) + \varepsilon_{ijk}$$

The parameter  $\theta_{21}$  is the population mean of  $EC_{50}$ . The parameter  $\theta_{22}$  is the population mean of maximum effect (Emax) with an associated random effect of  $\eta_{1,i}$ . The treatment

effect ( $\theta_1$ ) may or may not be included in the Emax model. The other parameters are the same as described earlier in the linear mixed effect model.

The goodness-of-fit of the Emax model will be compared with the linear mixed effect model through review of the AIC criteria, the parameter estimates, residual plots, concentration-QTc quantile plots (described below) and other diagnostic plots.

#### **5.2.4. Mixed Models Repeated Measures (MMRM) Analysis**

*Change from baseline in QTcF intervals will be analyzed using a MMRM model with sequence, period, treatment, time (post-dose timepoint) and treatment by time interaction as fixed effects, participants as a random effect, and baseline QTcF as the covariate. A compound symmetry covariance matrix will be fitted to the repeated times within participant (other covariance matrices will be considered if necessary), and the Kenward-Roger approximation will be used for estimating degrees of freedom. The ECG analysis set will be used for the MMRM analysis.*

Standard SAS output will be provided to support the statistical summary table for the analysis model, but will not be included in the CSR.

Example SAS code is provided in [Appendix 2](#).

#### Statistical Model Diagnostics

The presence of outliers will be investigated for this model. An outlier will be defined as any response data value with a studentized (conditional) residual greater than 3, or less than -3. A listing will be presented of any participants meeting these criteria and will be included with standard SAS output. The assumptions of normality will be verified graphically using residual plots. For each fitted model, a set of conditional studentized residual plots will be produced, including residual plot, histogram of normality, quantile-quantile (Q-Q) plot and summary of fit statistics. The residual plots will not be included in the CSR.

If there are outliers or major deviations from normality, then the effect of these on the conclusions may be investigated through alternative transformations and/or analyses excluding outliers. Justification for any alternative to the planned analysis will be given in the report of the study.

#### **5.3. Missing Data**

For the analysis of safety endpoints, the sponsor data standard rules for imputation will be applied.

In all PK data presentations (except listings), concentrations below the limit of quantification (BLQ) will be set to zero.

In listings, BLQ values (for PK or PD) will be reported as “<LLOQ”, where LLOQ will be replaced with the value for the LLOQ.

For PK and PD summary tables and plots of median profiles, statistics will be calculated having set concentrations to missing if one of the following cases is true:

1. A concentration has been collected as ND (i.e. not done) or NS (i.e. no sample),
2. A deviation in sampling time is of sufficient concern or a concentration has been flagged anomalous by the pharmacokineticist/statistician.

## 6. ANALYSES AND SUMMARIES

### 6.1. Primary Endpoint(s)

#### 6.1.1. *Placebo-corrected, baseline adjusted QTc interval using Fridericia's correction method (QTcF) of sisunatovir at expected maximum concentrations (Cmax) at the CCI [REDACTED].*

##### 6.1.1.1. Main Analysis

Change from baseline in QTcF at Day 3 and 4 post-dose will be analyzed by c-QT analysis as described in Section 5.2.3 using the cQTc analysis set. The final c-QTc model parameters will be presented in tabular format showing the estimate, standard error of the estimate, and 95% confidence interval. Goodness-of-fit plots will be presented for the final c-QTc model. A visualization displaying the model predicted mean  $\Delta\Delta\text{QTcF}$  and the 90% confidence interval will also be created.

Results of the model-based c-QTc analyses will be summarized in the CSR. More details of the model-based analyses, such as exploratory plots, model evaluations, and model fitting statistics, will be documented in a separate report and included as an Appendix to the CSR.

##### 6.1.1.2. Sensitivity/Supplementary Analyses

By time analysis (intersection-union test) will be provided as the supplementary analyses. Briefly, change from baseline in QTcF will be analyzed by MMRM as described in Section 5.2.4 using ECG analysis set. All planned post-dose time points on Day 3 and 4 of each period will be included in the model. The least-squares (LS) means of change from baseline QTcF of sisunatovir and placebo, as well as the  $\Delta\Delta\text{QTcF}$ , 5.2.1 and the corresponding 90% CIs will be reported for each post-dose timepoint. The LS means and 90% CI of  $\Delta\Delta\text{QTcF}$  (Y-axis) will be plotted against time post dose (X-axis).

### 6.2. Secondary Endpoint(s)

#### 6.2.1. *Adverse event (AE), ECG assessments, vital sign measurements, and clinical safety laboratory measurements.*

Analysis of AE, ECG assessments, vital sign measurements and clinical safety laboratory measurements will use the Safety Analysis Set defined in Section 4 unless otherwise stated.

##### 6.2.1.1. Adverse event (AE)

Adverse events will be reported in accordance with the sponsor reporting standards.

### 6.2.1.2. ECG assessments

Absolute values and changes from baseline for the ECG parameters (ie, HR, PR interval, QT interval, QTcF, QTcB, and QRS complex) will be summarized by treatment group and timepoint according to sponsor reporting standards. Tables will be paged by parameter.

Maximum absolute values and changes from baseline for QTcF, QTcB, PR, and QRS, as well as the maximum and minimum absolute values of HR, will also be summarized descriptively by treatment group using categories as defined in [Appendix 1](#). Numbers and percentages of participants meeting the categorical criteria will be provided. All planned and unplanned postdose timepoints will be counted in these categorical summaries.

*If any of the 3 individual ECG tracings has a QTcF value  $\geq 500$  msec, but the mean of the triplicates is  $< 500$  msec, the data from the participant's individual tracing will be described in a safety section of the study report in order to place the  $< 500$  msec value in appropriate clinical context. However, values from individual tracings within triplicate measurements that are  $\geq 500$  msec will not be included in the categorical analyses unless the average from the triplicate measurements is also  $\geq 500$  msec.*

Individual participant profiles will be created for those participants meeting the sponsor's abnormality criteria – including absolute values, change from baseline and percent change from baseline. Listings of participants with any single post dose value  $> 500$  msec will also be produced for QTcF.

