- In anesthetized guinea pigs, there were no effects on the QT or QTc (QTcB and QTcF) interval at any dose following intravenous administration (successive dose of 1, 3, and 10 mg/kg). At the highest dose, where peak exposure to free sisunatovir was approximately 735 ng/mL (~4.7-fold the High Clinical Exposure of 200 mg Q12 x 5 days), a slight reduction in HR together with elevated arterial blood pressure, LVSP, LV +dP/dtmax (and dP/dtmax), RR, PR and QRS interval were observed compared to vehicle.
- In conscious telemetered dogs, oral doses of sisunatovir up to 120 mg/kg were evaluated for effects on BP, HR, lead II ECG (PQ, QT, QTc interval [QTcB and QTcV], QRS duration, and ECG waveform morphology), and body temperature. Changes in cardiovascular parameters were limited to a transient increase in HR noted from 12 to 16 hours postdose at ≥ 45 mg/kg with no concomitant changes in QT

or QTc interval and a slight increase in diastolic arterial pressure observed up to 12 hours postdose at ≥ 45 mg/kg. At 120 mg/kg, decreases in PQ interval were observed at 2 hours postdose in the absence of noticeable changes in any other ECG parameter. These values remained within the normal range in conscious dogs. Exposure estimates are based on another study, in which a single dose of 120 mg/kg in male dogs had a free C_{max} of approximately 489 ng/mL (~3.1-fold the High Clinical Exposure of 200 mg Q12 x 5 days).

- Juvenile dogs dosed up 45 mg/kg QD for 3 weeks showed no effects on cardiovascular parameters (free C_{max} of 399 ng/mL). Dogs dosed up to 120 mg/kg QD for 14 days showed no effects on cardiovascular parameters (free C_{max} of 707 ng/mL; ~4.5-fold the High Clinical Exposure of 200 mg Q12 x 5 days). Dogs dosed up to 15 mg/kg QD for 28 days showed no test article related effects on ECG parameters. At 45 mg/kg/day decreases in group mean HR and increases in RR, PR, QT, and QTcV interval were noted, although individual values were within the normal range for animals of this age. It should be noted that the observed increase in QTcV interval in females was likely due to a notable increase of approximately 20-30 msec from predose in two females.

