7. Previous administration with an investigational product (drug or vaccine) within 30 days (or as determined by the local requirement) or 5 half-lives preceding the first dose of study intervention used in this study (whichever is longer).

Diagnostic Assessments:

8. A positive urine drug test.
9. For females, pregnancy, as indicated by a positive serum pregnancy test at screening and/or positive urine pregnancy test in WOCBP at Day -1.
10. Screening supine BP ≥ 140 mm Hg (systolic) or ≥ 90 mm Hg (diastolic), following at least 5 minutes of supine rest. If BP is ≥ 140 mm Hg (systolic) or ≥ 90 mm Hg (diastolic), the BP should be repeated 2 more times and the average of the 3 BP values should be used to determine the participant's eligibility.
11. Standard 12-lead ECG that demonstrates clinically relevant abnormalities that may affect participant safety or interpretation of study results (eg, QTcF >450 ms, complete LBBB, signs of an acute or indeterminate- age myocardial infarction, ST-T interval changes suggestive of myocardial ischemia, second- or third- degree AV block, or serious bradyarrhythmias or tachyarrhythmias). If the uncorrected QT interval is >450 ms, this interval should be rate-corrected using the Fridericia method only and the resulting QTcF should be used for decision making and reporting. If QTcF exceeds 450 ms, or QRS exceeds 120 ms, the ECG should be repeated twice and the average of the 3 QTcF or QRS values used to determine the participant's eligibility. Participants with an average QTc interval >450 milliseconds (ms) will not be allowed to participate in the study. Computer-interpreted ECGs should be overread by a physician experienced in reading ECGs before excluding a participant.
12. Participants with ANY of the following abnormalities in clinical laboratory tests at screening, as assessed by the study-specific laboratory and confirmed by a single repeat test, if deemed necessary:
 - GFR <60 mL/min/1.73m² based on CKD-EPI equation;
 - AST or ALT level $\geq 1.5 \times$ ULN;
 - Gamma-GT $> 1.2 \times$ ULN;

- Alkaline phosphatase $> 1.2 \times$ ULN;
- Total bilirubin level $\geq 1.5 \times$ ULN; participants with a history of Gilbert's syndrome may have direct bilirubin measured and would be eligible for this study provided the direct bilirubin level is \leq ULN.

Other Exclusion Criteria:

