10.8. Appendix 8: ECG Findings of Potential Clinical Concern

ECG Findings That May Qualify as AEs

Marked sinus bradycardia (rate <40 bpm) lasting minutes.New PR interval prolongation >280 ms.New prolongation of QTcF to >480 ms (absolute).New prolongation of QTcF by >60 ms from baseline.New-onset atrial flutter or fibrillation, with controlled ventricular response rate: ie, rate <120 bpm.New-onset type I second-degree (Wenckebach) AV block of >30 seconds duration.Frequent PVCs, triplets, or short intervals (<30 seconds) of consecutive ventricular complexes.
ECG Findings That May Qualify as SAEs

QTcF prolongation >500 ms.Absolute value of QTcF >450 ms AND QTcF change from baseline >60 ms.New ST-T changes suggestive of myocardial ischemia.New-onset LBBB (QRS complex >120 ms).New-onset right bundle branch block (QRS complex >120 ms).Symptomatic bradycardia.Asystole:
In awake, symptom-free participants in sinus rhythm, with documented asystolic pauses ≥ 3 seconds or any escape rate <40 bpm, or with an escape rhythm that is below the AV node.In awake, symptom-free participants with atrial fibrillation and bradycardia with 1 or more asystolic pauses of at least 5 seconds or longer.Atrial flutter or fibrillation, with rapid ventricular response rate: rapid = rate >120 bpm.

- Sustained supraventricular tachycardia (rate >120 bpm) (“sustained” = short duration with relevant symptoms or lasting >1 minute).
- Ventricular rhythms >30 seconds’ duration, including idioventricular rhythm (HR <40 bpm), accelerated idioventricular rhythm (HR >40 bpm to <100 bpm), and monomorphic/polymorphic ventricular tachycardia (HR >100 bpm [such as torsades de pointes]).
- Type II second-degree (Mobitz II) AV block.
- Complete (third-degree) heart block.

ECG Findings That Qualify as SAEs

- Change in pattern suggestive of new myocardial infarction.
- Sustained ventricular tachyarrhythmias (>30 second duration).
- Second- or third-degree AV block requiring pacemaker placement.
- Asystolic pauses requiring pacemaker placement.
- Atrial flutter or fibrillation with rapid ventricular response requiring cardioversion.
- Ventricular fibrillation/flutter.
- At the discretion of the investigator, any arrhythmia classified as an adverse experience.

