#### Categories for PR

Absolute Maximum (msec)	$\geq 300$	
Maximum Increase from Baseline (msec)	Baseline $> 200$ and max. increase $\geq 25\%$	Baseline $\leq 200$ and max. increase $\geq 50\%$

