#### Categories for QRS

Absolute Maximum (msec)	$\geq 140$
Maximum Increase from Baseline (msec)	max. increase $\geq 50\%$

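### The SAP's QRS categories leave a band between 120 and 140 ms uncounted for any baseline above 80 ms, although the protocol itself works with 120 ms

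*SAP*

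**What the plan says.** Protocol 9.3.1.2 sets no cut-offs for PR and QRS and leaves them to the SAP. SAP 6.2.1.2 then states that "Maximum absolute values and changes from baseline for QTcF, QTcB, PR, and QRS, as well as the maximum and minimum absolute values of HR" will be summarised by treatment using the categories in SAP Appendix 1, with numbers and percentages of participants, and with unplanned post-dose readings included.

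SAP Appendix 1 gives these categories:

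- **QRS:** an absolute maximum of at least 140 ms, or "max. increase $\geq 50" per cent.
- **PR:** an absolute maximum of at least 300 ms, or "Baseline $> 200$ and max. increase $\geq 25" per cent, or "Baseline $\leq 200$ and max. increase $\geq 50" per cent.

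The protocol uses lower figures elsewhere:

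- **Protocol 5.2, criterion 11:** "If QTcF exceeds 450 ms, or QRS exceeds 120 ms, the ECG should be repeated twice", and the average of the three values then decides eligibility.
- **Protocol Appendix 8** (ECG Findings of Potential Clinical Concern): "New-onset LBBB (QRS complex >120 ms", with the same 120 ms figure for right bundle branch block. Both are findings that may qualify as SAEs.
- **Protocol Appendix 8:** "New PR interval prolongation >280 ms", a finding that may qualify as an AE.

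SAP Appendix 1 also describes its classes as being of potential clinical concern. It does not say why its cut-offs differ from those in protocol Appendix 8.

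**The concern.** A categorical table exists to count individual outliers that a mean can hide. Here the QRS table starts counting at 140 ms for most plausible baselines. A participant could cross the value that would have triggered a repeat ECG at entry and still not be counted.

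ECG assessments belong to the secondary safety endpoint, and PR and QRS are an exploratory objective. There is also some nonclinical reason to look. In anaesthetised guinea pigs at the highest dose, elevations in a list of measures ending in "RR, PR and QRS interval were observed compared to vehicle". At stake is whether a zero in the QRS rows can be read as no participant having moved into an abnormal range. As the rows stand, it cannot be read that way.

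**Working it through.** The plan states no figure for this point, so there is nothing to reproduce. The check has three parts.

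**1. QRS trigger by baseline.** For baseline b, the lowest post-dose value that enters a SAP category is T(b) = min(140, 1.5b). This exceeds 120 when 1.5b > 120, that is, when b > 80. Values above 120 and below T(b) are uncounted.

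| Baseline (ms) | SAP trigger (ms) | Rise needed (ms) | Uncounted band (ms) |
|---|---|---|---|
| 80 | 120 | 40 | none |
| 85 | 127.5 | 42.5 | >120 to <127.5 |
| 90 | 135 | 45 | >120 to <135 |
| 94 | 140 | 46 | >120 to <140 |
| 100 | 140 | 40 | >120 to <140 |
| 110 | 140 | 30 | >120 to <140 |
| 120 | 140 | 20 | >120 to <140 |

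Example: a rise from 100 to 139 ms is +39%, below both rows, and is not counted.

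**2. Size for QRS.** The documents give no human QRS distribution, so these inputs are assumptions: normal baseline with mean (SD) 90 (8), 95 (9) or 100 (9) ms, truncated at 120 ms; one post-dose reading equal to baseline plus a uniform shift plus noise with SD 4 ms. Results by simulation, as % above 120 ms / % in a SAP QRS category:

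| Shift | Mean 90 | Mean 95 | Mean 100 |
|---|---|---|---|
| 0 ms | 0.04 / 0 | 0.4 / 0 | 1.2 / 0 |
| +15 ms | 4.7 / 0.002 | 15.3 / 0.04 | 29.6 / 0.13 |
| +20 ms | 13.2 / 0.03 | 30.4 / 0.36 | 49.3 / 1.2 |

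With 42 participants and +15 ms, the expected number above 120 ms is between 42 × 0.047 = 2.0 and 42 × 0.296 = 12.4. The expected number in a SAP category is at most 42 × 0.0013 = 0.05. The SAP takes the maximum over several readings, which would raise every entry somewhat, including the background in the 0 ms row.

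**3. PR trigger by baseline.** For b ≤ 200 it is min(300, 1.5b); for b > 200 it is min(300, 1.25b).

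| Baseline (ms) | SAP trigger (ms) | Against 280 ms |
|---|---|---|
| 160 | 240 | below |
| 180 | 270 | below |
| 186 | 279 | below |
| 190 | 285 | above |
| 200 | 300 | above |
| 201 | 251.25 | below |
| 220 | 275 | below |
| 225 | 281.25 | above |

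The trigger lies above 280 ms only for baselines of about 187–200 ms and from 225 ms up. Assume baseline mean 160 (SD 20) ms and noise SD 8 ms. A +40 ms shift then puts 0.26% in a SAP PR category and 0.01% above 280 ms. At +60 ms the figures are 7.8% and 0.26%. A row at >280 ms would add less than 0.01 percentage points at +40 ms and 0.02 at +60 ms. With mean 170 (SD 22) it would add 0.12 and 0.18 points.

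**The case against.** **The 120 ms figure is not a stand-alone on-treatment limit.** In protocol Appendix 8 it is attached to new bundle branch block, and in criterion 11 it triggers a repeat at eligibility. Appendix 8 serves event alerts, the SAP table serves tabulation, and protocol 9.3.1.2 expressly hands the categories to the SAP. This stands: the two documents do not contradict each other, and the point is about the usefulness of the table.

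**Other analyses cover a conduction effect.** SAP 6.2.1.2 summarises PR and QRS by treatment and time point. SAP 6.3.1 gives time-matched differences from placebo with 90% CIs and plots. With noise SD 4 ms and 42 participants, the half-width is about 1.683 × 4 × √(2/42) = 1.5 ms, so a uniform 15 ms shift would be plain. Protocol 9.3.4 also says that ECG abnormalities of potential clinical concern will be described. This largely stands. A reader might infer that the plan cannot register a conduction effect, or that the zeros would mislead; the documents do not support that. What remains is that means do not count individuals, Appendix 8 findings only may qualify as events, and SAP 6.2.1.2 promises a threshold listing for QTcF alone.

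**The animal signal is weak support for any particular effect size.** The protocol gives no magnitudes. The guinea-pig finding was at about 4.7-fold the high clinical exposure. PR rose in the 28-day dog study, but individual values were within normal range, and PQ shortened in telemetered dogs. Study C5241004 found no clinically significant QRS change and no PR concern. This stands: the shifts in the working are illustrations, not predictions.

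**Conclusion.** The gap in the QRS categories is real and follows from the cut-offs alone: for every baseline above 80 ms there are values above 120 ms that enter no category, and from about 94 ms the gap is the full 121–139 ms. Its size in participants depends on assumed baselines. For a 15 ms shift it is roughly 5–30% above 120 ms against at most 0.13% counted, with at most 1.2% above 120 ms at a single reading when there is no shift.

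Two stronger readings are tempting. One is that the PR categories share the fault. They do not, because the percentage rows already trigger below 280 ms for baselines up to 186 ms and, under the assumptions above, catch more participants than a 280 ms line would. The difference between 300 and 280 ms is a matter of consistency. The other is that PR above 200 ms is a limit the plan has overlooked. In these documents 200 ms is only the SAP's baseline stratum, and no section sets it as a limit of concern.

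This is a modest improvement to a descriptive safety table. It does not touch the primary concentration–QTc analysis or the moxifloxacin assay-sensitivity test.

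**What to change.** Add one row to the QRS categories in SAP Appendix 1: new QRS >120 ms in participants whose period baseline is ≤120 ms, tabulated by treatment beside the two existing rows.

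For PR, reconcile the ≥300 ms row with the >280 ms entry in protocol Appendix 8, or add a sentence saying why the tabulation and the alert list differ. No PR >200 ms row is needed.

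The data are already collected, so the cost is SAP wording and a little programming. The downside is a slightly longer table with small background counts in all three arms, which the placebo column lets the reader judge.
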